**Inclusion Criteria:**

- Age 14 – 45 years.
- History of post-traumatic headache or neck pain following a concussion or head injury within the last 2 years.
- Self-reported lack of meaningful benefit with at least one previous treatment trial. Previous treatment could include a migraine prophylactic medication, a neuropathic pain medication, a physical intervention, or a cognitive-behavioral intervention.

**Exclusion Criteria:** Subjects will be excluded in the following circumstances:

- Significant underlying psychological concerns, as determined by study psychologist up on review of standardized assessment
- Lack of parental consent and child assent (if patient age <18 years) or lack of consent (if patient age >18 years). Unable to complete the questionnaire, based on parental or patient estimation of cognitive or language limitations

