**3. Description of Study Treatments or Exposures/Predictors**

Patients enrolled in the study will be randomized to receive either an ONB (Figure 2, additional procedure details provided below) with dexamethasone 2mg each site with 3ml 1% lidocaine, for a total of two sites or a CMBB (Figure 3a & 3b, additional procedure details provided below) with dexamethasone 1.5mg each site with 2 ml 1% lidocaine, for a total of three sites on each side. The assignment of the procedure will be randomized however neither the patients nor the investigator will be blinded to the procedure. If patients exhibit a  $\geq 50\%$  pain reduction on receiving the block evaluated after four weeks, then they may continue to receive blocks as needed, but not more than one every three months. If patients exhibit  $< 50\%$  pain reduction, the patient will be treated as per the clinician's judgment with the possibility of a cross over to the other treatment option in the protocol.

All patients will be followed for 12 months after enrollment and after the crossover of treatments they will continue to be treated and followed per clinical standard of care.

As part of this study, patients will need to complete 8 follow-up visits, of which the first and second will be in-person clinical visits and the other follow-ups could either be conducted in-person at the clinic or via teleconference - video:

a) Visit 1: in-person clinic visit

- At the first visit to the clinic, the physician or nurse will verify the patient's name and date of birth, and will collect information about pain, current and past medicines, and general health. The physician will perform a physical examination and measure heart rate, blood pressure and respiratory rate, and conduct a neurological exam.
- Baseline questionnaires will be taken, including Pain (NRS), Concussion Symptom Score, MIDAS/PedMIDAS, Anxiety, Depression, FDI, and QL.

At the end of the visit, all enrolled patients will be randomized to one of the two minimally invasive procedures, the ONB or the CMBB. Information from the patient's most recent clinical visit note (retrieved from the patient's medical record) may be used to obtain Visit 1 data.

b) Visit 2: Cervical and medial branch block procedures

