The procedure will be performed at Boston Children's Hospital or Beth Israel Deaconess Medical Center or Mass General Brigham Operation Room. Patients may receive sedation as per clinical need, and procedures will be performed in a standardized manner. Neither the patient nor the investigator will be blinded to the type of procedure.

Patients will not be universally sedated however a particular subset of patients may receive sedation. Pediatric patients and some adults with extreme anxiety to procedures will receive mild IV sedation with fentanyl, midazolam and occasionally propofol. This is not general anesthesia but is Monitored Anesthesia Care (MAC). Patients will be awake enough to report any symptoms or discomfort. Anesthesia will be administered either in an Operating Room or Day Surgery Unit setting of the study sites and not in an outpatient setting. A separate anesthesia team consisting of an anesthesiologist and nurse anesthetist (CRNA) will be responsible for administration of anesthesia and airway maintenance. Vital signs will be monitored every 5 minutes and anesthesia adjusted based on patient discomfort.

Details on doses of dexamethasone and lidocaine to be used:

Dexamethasone doses:

Occipital nerve block: 2 mg / block

Cervical facet injections/medial branch block: 1.5 mg / facet joint

Lidocaine doses:

Occipital nerve block: 3 ml of 1% lidocaine / block

Cervical facet injections/medial branch block: 2 ml of 1% lidocaine / facet joint

DESCRIPTION OF OCCIPITAL NERVE BLOCK:

The patient will be in the seated position. The back of the head (occipital area) will be prepped with alcohol pads. Following this, the left or right greater occipital nerve will be accessed at the midpoint of the occipital protuberance and the mastoid process using a 25-gauge 1-1/2 inch needle. 1% lidocaine will be used for skin and subcutaneous analgesia. Following this, area of the left greater occipital nerve will be accessed and the injection fanned. A mixture of 2 mg of dexamethasone and 3 ml of 1% lidocaine will be injected into this area. Following this, the contralateral side will be addressed in a similar fashion (if patient needs bilateral injection). A total of 4 mg of dexamethasone and 6 mL of 1% lidocaine will be injected. The patient will be observed in recovery for complications of bleeding, worsening of symptoms, or paresthesias.

DESCRIPTION OF CERVICAL FACET / MEDIAL BRANCH BLOCK:

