The patient will be placed in the prone position in the procedure room on a Steris table with fluoroscopy. The back of the neck will be prepped and draped in the usual sterile fashion with ChloraPrep. Under fluoroscopy guidance the high cervical facets will be visualized in AP, oblique and lateral views. Using a 22-gauge, 2-1/2-inch spinal needle, the left C 4-5 facet joint/medial branch area will be accessed under fluoroscopy. 1% lidocaine will be used for the skin and subcutaneous analgesia. Contrast omnipaque 300 mg/ ml, 0.5 ml will be used to confirm the needle position. Similar procedures will be repeated at C2-3 and C 3-4 levels. Similar procedures will be done on the corresponding levels on the contralateral side. Dexamethasone 1.5 mg with 2 mL of 1% lidocaine will be injected at each of these levels. A maximum of 9 mg of dexamethasone will be used. The patient will be observed in recovery for complications of bleeding, worsening of symptoms or paresthesias.

After the procedure is completed, all patients will recover in the Post Anesthesia Care Unit (PACU). Patients will be examined and they will be required to complete questionnaires. Patients will be discharged from the hospital per hospital guidelines and standard of clinical practice.

c) Visit 3 to 8: in-person visit or tele-conference

At 1, 2, 3, 6, 9, and 12 months after enrollment, patients will be evaluated to determine how well they did after the procedures. This would include the same steps from previous appointments. If the study treatment has been helpful, the physician might decide to continue the treatment with the procedures as needed. Clinical criteria and patient – physician agreement would be used to determine next steps in the patient's treatment plan.

d) E-mail questionnaires:

During the first two months of the study, patients will be contacted by our research team via email on a weekly basis requesting them to complete a short questionnaire that includes questions about their pain scores (NRS), MIDAS/ PedMIDAS, QL, FDI, Anxiety, Depression, and Concussion Symptoms Score. After the initial 2 months on the study, we will continue to contact patients every 2 weeks over the next 10-months (follow-ups over a total of 12 months). See Table 1 below for REDCap survey schedule.

[figure not shown]
Table 1: Schedule of REDCap surveys

Follow-Up	Questionnaire
Week 0	Migraine disability
	Pain Assessment
	Concussion Score
	General functionality
	Quality of Life
	Anxiety
	Depression

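### Suitability for both blocks is not checked as an entry condition, and the plan deals with unsuitability by removing the patient from the study, possibly after open allocation

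*Combined protocol and SAP*

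**What the plan says.** **Eligibility (section D.2).** The inclusion criteria cover age 14 to 45, a history of post-traumatic headache or neck pain, and lack of benefit from at least one earlier treatment. The exclusion list, introduced by "Subjects will be excluded in the following circumstances", covers psychological concerns, consent or assent, and ability to complete the questionnaire. Neither list mentions fitness for either injection.

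**Allocation (section D.3, Visit 1).** At the end of the visit, "all enrolled patients will be randomized to one of the two minimally invasive procedures, the ONB or the CMBB". Earlier in the same visit, general health and medicines are recorded and "The physician will perform a physical examination and measure heart rate, blood pressure and respiratory rate, and conduct a neurological exam". No sentence makes randomisation depend on what is found.

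**The two procedures (section D.3, Visit 2).** For ONB, "The patient will be in the seated position"; the site is found by surface landmarks, and no imaging or contrast is described. For CMBB, "The patient will be placed in the prone position in the procedure room on a Steris table with fluoroscopy", and "Contrast omnipaque 300 mg/ ml, 0.5 ml will be used to confirm the needle position". Neither patient nor investigator is blinded.

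**Later treatment (section D.3).** After a poor response, treatment follows the clinician's judgment. At the later visits, clinical criteria and patient and "physician agreement would be used to determine next steps".

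**Removal (section L).** A patient is taken out of the study, at whatever time, if the attending physician considers treatment inappropriate for that patient's care.

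**Follow-up (section D.3).** "All patients will be followed for 12 months after enrollment".

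**The concern.** In ordinary practice a clinician picks the block to suit the patient. Randomisation takes that choice away, so trials usually ask before allocation whether each option could be given. Here that question is not an entry condition, and the two options make different demands on the patient.

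The result is that suitability may be settled after the allocation is known to everyone, and settled by ending the patient's participation. A patient who can have ONB but not CMBB would stay if allocated to ONB and leave if allocated to CMBB. The arms would then no longer be the groups that randomisation formed, and the 12-month outcomes of those removed would be lost. Because allocation is open, the judgment that treatment is inappropriate can also be influenced by knowing which block was assigned.

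Crossover and repeat blocks are outside this point, since the protocol already makes them subject to clinical judgment.

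**Working it through.** This is mainly a comparison of passages; only the scale needs arithmetic.

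**Step 1: is suitability an entry condition?** The six subjects in section D.2 are age, headache or neck-pain history, earlier treatment, psychological concerns, consent or assent, and ability to complete the questionnaire. None concerns suitability for a block. Visit 1 collects relevant information before randomisation, but no rule connects it to eligibility.

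**Step 2: do the arms differ in what they demand?**

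| | ONB | CMBB |
|---|---|---|
| Position | Seated | Prone |
| Guidance | Surface landmarks | Fluoroscopy in three views |
| Contrast | None described | 0.5 mL to confirm needle position, procedure repeated at other levels |

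If contrast is used at each of three levels on both sides, the CMBB total is 3 × 2 × 0.5 mL = 3 mL. For ONB as described it is 0.

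**Step 3: when can section L act?** At any time, so there are three cases.

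- Before randomisation at Visit 1: the patient is never allocated and the comparison is untouched.
- Between allocation and the procedure at Visit 2: the patient is not injected, but leaves after an open allocation.
- After the procedure: the patient leaves with partial data.

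Only the first case keeps the randomised comparison intact, and nothing in the protocol steers cases towards it.

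**Step 4: does removal fit the rest of the plan?** Section D.3 follows all patients for 12 months; section L removes some. Section I compares the two randomised groups, but defines no analysis population and does not say how a removed patient is counted.

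**Step 5: scale.** Section I gives 24 per group, so 48 in total, and a planned enrolment of 63. Equal groups imply 63/2 = 31.5 per arm. One removal is 1/31.5 = 3.2% of an arm. The margin for dropout is 63 − 48 = 15 patients, so a few removals would hardly affect power. What matters is that they could fall on one side. How many there would be cannot be derived from the documents.

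**The case against.** The strongest reply is that the safeguard already exists. Section L is a written physician-judgment rule, it directs removal, and it can act before allocation or in the interval before Visit 2. The protocol relies on the same kind of judgment for crossover and repeat blocks. Both procedures are described as standard of care and take place in hospital facilities, and Visit 1 already includes a history and examination. A line in section D.2 would mostly formalise what clinicians are likely to do anyway. This stands, and it is why the priority is low.

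A reader might infer that the trial will treat patients with CMBB who should not have it. The documents do not support that. They support possible allocation; treatment would require both the Visit 1 assessment and section L to fail.

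A reader might also supply a risk group, such as pregnant patients or those with an earlier contrast reaction. The documents name no group unsuitable for CMBB alone, so the point does not rest on one. Equally, an assumed number of unsuitable patients could be combined with the one-in-two chance of allocation to CMBB to give impressive probabilities. They would reflect only the assumed number and are not evidence.

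Finally, the tension between removal and follow-up applies to withdrawal for any reason, and section D.1 speaks of patients remaining up to 12 months. Both remarks are fair. But unsuitability for one block is a reason for removal that plausibly differs between arms, and section D.3 states the 12-month follow-up without exception. What survives is the timing and consequence of the removal rule, not a claim of unprotected patients.

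**Conclusion.** The point holds in a limited form. Suitability for both blocks is not required before randomisation, although only CMBB involves the prone position, fluoroscopy and contrast. Unsuitability is handled by removal from the study, which may follow an unblinded allocation and conflicts with following all patients for 12 months.

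That removals would be more frequent in the CMBB arm is an inference from the procedure descriptions, not from data. The 3.2% per removal assumes 63 patients in equal arms. No rate of unsuitability and no size of bias can be given. A reader might infer material bias in the treatment comparison; nothing in the documents establishes it.

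This is a cheap improvement of low priority.

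**What to change.** 1. **Section D.2.** Add that, at Visit 1 and before randomisation, the physician confirms and records that the patient can receive either block as described in section D.3. Patients who cannot are recorded as screen failures and are not randomised. The investigators should set the clinical content of the check.
2. **Section L.** Change the removal rule so that a randomised patient whose treatment is withheld or stopped discontinues the treatment only, stays in the 12-month follow-up, and is analysed in the group to which he or she was randomised.

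The cost is one eligibility line, one recorded confirmation at a visit that already includes a history and examination, and one amended sentence. The downside is a few more screen failures and slightly narrower eligibility.

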Week 1	Pain Assessment
	Concussion Score
	General Functionality
	Side Effects Related to Invasive Treatment
Week 2	Pain Assessment
	Concussion Score
	General Functionality
	Side Effects Related to Invasive Treatment
Week 3	Pain Assessment
	Concussion Score
	General Functionality
	Side Effects Related to Invasive Treatment
Improvement Evaluation 1m	Pain Assessment
	Concussion Score
	General Functionality

[figure not shown]
	Side Effects Related to Invasive Treatment Improvement Additional Procedures
Week 5	Pain Assessment Concussion Score General Functionality Side Effects Related to Invasive Treatment
Week 6	Pain Assessment Concussion Score General Functionality Side Effects Related to Invasive Treatment
Week 7	Pain Assessment Concussion Score General Functionality Side Effects Related to Invasive Treatment
Improvement Evaluation 2m	Pain Assessment Concussion Score General Functionality Side Effects Related to Invasive Treatment Quality of Life Anxiety Depression Improvement Additional Procedures
Week 10	Pain Assessment Concussion Score General Functionality Side Effects Related to Invasive Treatment
Improvement Evaluation 3m	Migraine disability Pain Assessment Concussion Score General Functionality Side Effects Related to Invasive Treatment Quality of Life Anxiety Depression Improvement Additional Procedures
Week 14	Pain Assessment Concussion Score General Functionality Side Effects Related to Invasive Treatment
Week 16	Pain Assessment Concussion Score General Functionality

	Side Effects Related to Invasive Treatment
Week 18	Pain Assessment Concussion Score General Functionality Side Effects Related to Invasive Treatment
Week 20	Pain Assessment Concussion Score General Functionality Side Effects Related to Invasive Treatment
Week 22	Pain Assessment Concussion Score General Functionality Side Effects Related to Invasive Treatment
Improvement Evaluation 6m	Migraine disability Pain Assessment Concussion Score General Functionality Side Effects Related to Invasive Treatment Quality of Life Anxiety Depression Improvement Additional Procedures
Week 26	Pain Assessment Concussion Score General Functionality Side Effects Related to Invasive Treatment
Week 28	Pain Assessment Concussion Score General Functionality Side Effects Related to Invasive Treatment
Week 30	Pain Assessment Concussion Score General Functionality Side Effects Related to Invasive Treatment

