#### **J. Adverse Event Criteria and Reporting Procedures**

Adverse or unanticipated events will be reported as required to the Boston Children's Hospital and other site IRB's according to institutional reporting requirements. An adverse event log will be used to document adverse events.

An Adverse Event (AE) refers to any untoward medical occurrence associated with the use of Amitriptyline, whether or not considered drug related, as described in 21 CFR 312.32. We will monitor and report any AEs, as guided in 21 CFR 312.32.

The intensity (grade) of each AE will be assessed using the following scale:

- i. Grade 1 (Mild): Experiences which are usually transient, requiring no special treatment, and do not interfere with the subject's daily activities.
- ii. Grade 2 (Moderate): Experiences which introduce some level of inconvenience or concern the subject, and may somewhat interfere with daily activities, but are usually ameliorated by simple therapeutic measures (may include drug therapy).
- iii. Grade 3 (Severe): Experiences which are unacceptable or intolerable, significantly interrupt the subject's usual daily activity, and require systemic drug therapy or other treatment.
- iv. Grade 4 (Life-threatening): Experiences which cause the subject to be in imminent danger of death.
- v. Grade 5 (Death): Subject fatality

If the intensity (grade) changes within a day, the maximum intensity (grade) should be recorded. If the intensity (grade) changes over a longer period of time, the changes should be recorded as separate events (having separate onset and stop dates for each grade).

Relationship to the medication or procedure administration will be determined by the Investigator according to the following criteria:

- i. Unexpected/Expected Adverse Drug Events
  - a. Unexpected: Any adverse experience, the nature, severity or frequency of which is not consistent with the risk information described in the investigational plan or protocol or consent form. Unexpected refers to an experience that has not been previously observed. This includes events that are more serious than expected or occur more frequently than expected.
  - b. Expected: Those experiences that have been identified in nature, severity, or frequency in the current investigator brochure, investigational plan/protocol and current consent form.
- ii. Relatedness
  - a. Unrelated: The adverse event is clearly not related to the investigational agent

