  - b. Unlikely: The adverse event is doubtfully related to the investigational agent
  - c. Possible: The adverse event may be related to the agent

- d. Probable: The adverse event is likely related to the investigational agent
- e. Definite: The adverse event is clearly related to the investigational agent

For the purpose of safety analyses, all AEs that are classified as possible, probable or definite will be considered treatment-related events.

We regard the following as AEs for ONB and CMBB procedures:

- Neurotoxicity: The injection of anesthetics or steroids, or meningeal inflammation from the breech of the spinal canal during the procedure with or without direct neural injury can result in arachnoiditis or cauda equina syndrome. We regard these risks to be extremely low.
- Neurological injury: Direct mechanical injury to the spinal nerves or the spinal cord itself can occur during needle placement for injections. We regard these risks to be extremely low.
- Vascular injury: Unintentional vascular injection of the steroid and local anesthetic suspension will result in medications simply being carried away from the site of inflammation, thus reducing any local anti-inflammatory effect. In contrast, intra-arterial injection is far less common, but may cause catastrophic neurologic injury and seizures. We regard these risks to be extremely low.
- Pharmacologic effects of corticosteroids: The administration of exogenous corticosteroids can lead to both hypercortisolism and suppression of the adrenal cortex's normal production of endogenous glucocorticoids. The long-acting corticosteroid preparations used for injections slowly release the active steroid over 1 to 3 weeks. Fluid retention, weight gain, increased blood pressure and cushingoid side effects have been reported. Glucocorticoid administration reduces the effect of insulin and results in increased blood glucose levels and insulin requirements in diabetics for 48 to 72 hours. Although rare, allergic reaction to systemic administration of corticosteroid has also been documented. We regard these risks to be extremely low.
- Bleeding complications: Injections for pain treatment carries the risk of bleeding in patients without any apparent coagulopathy. Significant bleeding can cause compression of surrounding structures, potentially resulting neurological problems and worsening pain. We regard these risks to be extremely low.

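### The only safety item in the survey schedule is titled for treatment-related side effects, which leaves the first causality judgment to unblinded patients

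*Combined protocol and SAP*

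**What the plan says.** Table 1 in Section D.3 lists the content of each REDCap survey. Every survey after Week 0 carries an item titled "Side Effects Related to Invasive Treatment", and no other item in the table concerns safety. The description of the e-mailed questionnaires in the same section lists pain, disability, quality of life, mood and concussion scores, but no safety question.

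Section J defines an adverse event as "any untoward medical occurrence associated with the use of Amitriptyline, whether or not considered drug related". Neither arm receives amitriptyline; events expected from the two blocks are listed later in the section. On causality, Section J states: "Relationship to the medication or procedure administration will be determined by the Investigator according to the following criteria". The scale has five levels and starts with "Unrelated: The adverse event is clearly not related to the investigational agent". For the safety analyses, "all AEs that are classified as possible, probable or definite will be considered treatment-related events".

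On other ways of finding events, Section J says that "An adverse event log will be used to document adverse events". Section D.3 says that at Visits 3 to 8 "patients will be evaluated to determine how well they did after the procedures", and that these visits repeat the steps of earlier ones.

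**The concern.** Section J works in two stages: events are collected, then the investigator grades relatedness. The second stage can only grade what the first delivers. An item that asks for related side effects moves part of the grading to the patient and to an earlier point, where it leaves no record.

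Patients are poorly placed to make that judgment here:

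- Some harms that Section J lists, such as fluid retention, weight gain and raised blood pressure, are not ones a patient would readily connect with an injection in the neck or scalp.
- Section J also defines unexpected events as ones not seen before. These are the hardest for a patient to recognise as related.
- After four weeks, repeat blocks, crossover and other treatment are allowed (Section D.3), so attribution becomes harder as follow-up goes on.
- Patients know their procedure, and the procedures look different: fluoroscopy-guided injections at three levels on each side, against one or two occipital injections. Readiness to attribute a symptom could differ by arm.

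Aim 5 concerns safety, and its hypothesis is that complications and side effects will be minimal. A low recorded rate would be hard to interpret if it partly reflected how the question was put.

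**Working it through.** No figure in the plan depends on this point, so the check is a count and a comparison of the passages.

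**1. Count of Table 1.** Post-baseline surveys by period:

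- to month 3: Weeks 1, 2, 3, month 1, Weeks 5, 6, 7, month 2, Week 10, month 3 = 10
- to month 6: Weeks 14, 16, 18, 20, 22, month 6 = 6
- to month 9: Weeks 26, 28, 30, 32, 34, month 9 = 6
- to month 12: Weeks 38, 40, 42, 44, 46, month 12 = 6

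Total 10 + 6 + 6 + 6 = 28. All 28 carry the item under the related-only title. None carries an item that is neutral on cause.

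**2. Surveys against visits.** Visits 3 to 8 fall at months 1, 2, 3, 6, 9 and 12, the nominal times of six of the surveys. That leaves 28 − 6 = 22 surveys at times with no scheduled visit. From month 3 the visits are three months apart.

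**3. Where delayed steroid effects would fall.** Section J describes steroid release from long-acting preparations over 1 to 3 weeks. If the procedure closely follows enrollment (an assumption, since visits are timed from enrollment), that period is covered by the surveys at Weeks 1, 2 and 3 and ends before the month 1 visit. An effect that resolves within it depends on the survey, or on recall at that visit.

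**4. Which events a patient filter would remove.** If the item works as titled, there are four cases:

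| | Investigator would grade possible, probable or definite | Investigator would grade unrelated or unlikely |
|---|---|---|
| Patient links it to the block | reported and counted as related | reported, graded down |
| Patient does not link it | may be missed; related count too low | may be missed; related count unchanged |

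The lower-left cell matters most, because it reduces the treatment-related count that Section J defines. The lower-right cell only under-fills the two lowest grades.

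**5. Other routes.**

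- *Visits 3 to 8.* The Visit 1 steps that they repeat include pain, medicines, general health and examination. None is limited to related events, but none is described as adverse event questioning. The visits may be held by video.
- *Procedure day.* A separate anesthesia team gives any sedation, vital signs are taken every 5 minutes, and patients are observed and examined in recovery. This covers immediate events.
- *Adverse event log.* Sections J and K say that it exists. Neither says what question, schedule or source feeds it, or how a survey answer enters it.

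**The case against.** The strongest objection is that the point rests on a title. The form's questions are not public, and it could be a neutral symptom checklist under a narrow heading. That stands, and it limits the conclusion to a risk. If the items are neutral, a new title and a line on routing would settle most of it.

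A reader might infer that events which patients do not attribute to the block never reach the investigator. The documents do not support that. Six clinician visits cover general health and examination, and sedation events are watched directly by clinical staff. The concussion, anxiety and depression scores carry no attribution condition, and a psychologist reviews the last two (Section K). A log is kept outside the survey. The risk lies mainly between visits.

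A reader might also infer a false difference in event rates between the arms. Section I specifies no comparison of adverse event rates by arm; its only specified safety comparison is of fluoroscopy time and radiation exposure. The items listed under Aim 5 (fluoroscopy and radiation, sedation method, anesthetic complications) come from procedural records and do not depend on this form. Arm-dependent attribution therefore affects how descriptive event counts are read, not a planned test, and its direction is unknown.

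Finally, the clause counting events whether or not related is written for amitriptyline, so read literally it sets no standard for the blocks. That is true and is a defect in itself. The mismatch does not depend on the clause: the causality step expressly covers procedures as well as medication, and its scale includes unrelated events.

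**Conclusion.** The point holds as a risk in the survey route. The title of the only scheduled safety item is narrower than the causality process in Section J. No text describes questioning that is neutral on cause at any contact, or the path from survey answer to log. Under-reporting is most plausible for events between visits that a patient does not link to the injection, and its extent may differ between arms.

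Its size is not estimable: the documents give no attribution rate, so any assumed share would be arbitrary. All 28 post-baseline surveys carry the item, 22 of them away from a scheduled visit. The conclusion assumes that the questions follow the title. It does not show that events are lost, and it does not touch the primary outcome or any specified between-arm test. The change is worth making because it is cheap and strengthens the trial's safety account.

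**What to change.** 1. Retitle and reword the survey item to ask for *any new or worse symptom or health problem since the last survey, whatever the cause*, with date and severity.
2. Ask the same question at Visits 2 to 8 and name it as a visit step.
3. State in Section J that survey and visit answers go to the adverse event log, and who transfers them.
4. Leave relatedness to the investigator, on the existing five-level scale.
5. Reconcile the Section J definition, which names amitriptyline, with the occipital and medial branch procedures.

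No Week 0 version is needed, since general health and symptom scores are already collected at baseline.

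The cost is a REDCap form edit, a line in the visit script and a short change to Section J. The downside is more minor events to log and grade. If the form is changed during follow-up, record the date, so that counts before and after are not read as one series.
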